8.3.1. Time Period and Frequency for Collecting AE and SAE Information

The time period for actively eliciting and collecting AEs and SAEs (“active collection period”) for each participant begins from the time the participant provides informed consent, which is obtained before the participant’s participation in the study (ie, before undergoing any study-related procedure and/or receiving study intervention), through and including a minimum of 28 calendar days after the last administration of the study intervention.

Follow-up by the investigator continues throughout and after the active collection period and until the AE or SAE or its sequelae resolve or stabilize at a level acceptable to the investigator and Pfizer concurs with that assessment.

For participants who are screen failures, the active collection period ends when screen failure status is determined.

If the participant withdraws from the study and also withdraws consent for the collection of future information, the active collection period ends when consent is withdrawn.

If a participant definitively discontinues or temporarily discontinues study intervention because of an AE or SAE, the AE or SAE must be recorded on the CRF and the SAE reported using the CT SAE Report Form.

Investigators are not obligated to actively seek AEs or SAEs after the participant has concluded study participation. However, if the investigator learns of any SAE, including a death, at any time after a participant has completed the study, and he/she considers the event to be reasonably related to the study intervention, the investigator must promptly report the SAE to Pfizer using the CT SAE Report Form.

8.3.1.1. Reporting SAEs to Pfizer Safety

All SAEs occurring in a participant during the active collection period as described in [Section 8.3.1](#) are reported to Pfizer Safety on the CT SAE Report Form immediately upon awareness and under no circumstance should this exceed 24 hours, as indicated in [Appendix 3](#). The investigator will submit any updated SAE data to the sponsor within 24 hours of it being available.

If a participant begins a new anticancer therapy, SAEs occurring during the above -indicated active collection period must still be reported to Pfizer Safety irrespective of any intervening treatment. Note that a switch to a commercially available version of the study intervention is considered as a new anticancer therapy for the purposes of SAE reporting.

8.3.1.2. Recording Nonserious AEs and SAEs on the CRF

All nonserious AEs and SAEs occurring in a participant during the active collection period, which begins after obtaining informed consent as described in [Section 8.3.1](#), will be recorded on the AE section of the CRF.

The investigator is to record on the CRF all directly observed and all spontaneously reported AEs and SAEs reported by the participant.

If a participant begins a new anticancer therapy, the recording period for nonserious AEs ends at the time the new treatment is started; however, SAEs must continue to be recorded on the CRF during the above-indicated active collection period. Note that a switch to a commercially available version of the study intervention is considered as a new anticancer therapy for the purposes of SAE reporting.

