#### **3.3. Safety Endpoints**

Safety endpoints will be summarized based on the on-treatment period unless otherwise specified.

On-treatment is defined as the time from the first non-zero dose of study treatment to the last non-zero dose + 28 days.

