##### **3.3.1. Adverse Events**

An adverse event is considered treatment emergent (TEAE) relative to a given treatment if the event occurs during the on-treatment period (regardless if it was seen prior to the start of treatment). An adverse event is considered treatment-related as assigned by the investigator.

Adverse events (AEs) will be coded to preferred term (PT) and system organ class (SOC) using the Medical Dictionary for Regulatory Activities (MedDRA) and classified by severity using the National Cancer Institutes (NCI) Common Terminology Criteria for Adverse Events (CTCAE), version 4.03. Adverse events occurring on the same day as the first dose of study treatment will be considered to have occurred during the on-treatment period. All other assessments which occur on the same day as the first dose of study treatment will be considered as baseline assessments.

Safety data collected outside the on-treatment period as described above will be listed but not summarized.

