### **Date of Start of New Anti-cancer Therapy**

Not applicable.

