## **6. ANALYSES AND SUMMARIES**

Analyses for B1371019 and B1371012 will be conducted separately and independently.

All participants who receive any study treatment (safety analysis set) will be included in the summaries and listings of safety data. Overall safety profile and tolerability of azacitidine or glasdegib + azacitidine will be characterized by type, frequency, severity, seriousness, timing, and relationship to study therapy of AEs.

AEs will be classified using the MedDRA classification system. The severity of the toxicities will be graded according to the NCI CTCAE version 4.03.

In all summaries, emphasis will be placed on TEAEs (events occurring from Amendment 6 consent up to last dose + 28 days). AEs will be summarized by the frequency of participants experiencing TEAEs corresponding to body systems and MedDRA preferred term and by worst NCI CTCAE (version 4.03) grade.

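### For participants who start new anticancer therapy within 28 days of last dose, nonserious AEs stop being recorded but SAEs do not, and the TEAE window neither stops nor flags events at that point

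*Protocol*

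**What the plan says.** **Recording.** Protocol 8.3.1 sets active AE and SAE collection from consent "through and including a minimum of 28 calendar days after the last administration of the study intervention". Protocol 8.3.1.2 then separates the two kinds of event when new anticancer therapy begins: "the recording period for nonserious AEs ends at the time the new treatment is started", but "SAEs must continue to be recorded on the CRF during the above-indicated active collection period". It adds that "a switch to a commercially available version of the study intervention is considered as a new anticancer therapy", and the same sentence confines that to SAE reporting purposes.

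**Analysis.** SAP 3.3: "On-treatment is defined as the time from the first non-zero dose of study treatment to the last non-zero dose + 28 days". SAP 3.3.1 makes any AE in that period treatment emergent. SAP 6 and Protocol 9.4.1 describe TEAEs as "events occurring from Amendment 6 consent up to last dose + 28 days". The two descriptions start at different points, but both end at last dose plus 28 days and neither mentions subsequent therapy. SAP 6.3.1 bases all AE analyses on TEAEs unless otherwise specified.

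**Date of the switch.** Under SAP 5.3.1, the entry "Date of Start of New Anti-cancer Therapy" is marked not applicable. So is SAP 6.2.5 on prior and subsequent anticancer therapies. The Schedule of Activities (Protocol 1.3) does not name this date among the CRF items, but refers to further CRFs described in a completion guide.

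**The concern.** The recording rule and the analysis window were not aligned. After a switch inside the 28 days, a serious event is recorded and tabulated as treatment emergent; a nonserious event on the same day need not be recorded at all. A TEAE table by maximum grade then mixes two ascertainment periods, and some of its serious events arose after another treatment had begun.

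The situation is foreseeable. Treatment runs until progression or relapse among other reasons (Protocol 6.1.3), and starting another anticancer treatment is a listed reason for discontinuation (Protocol 7.1). AEs and SAEs are the only endpoint of Amendment 6, and the tables feed US and EU results disclosure (SAP 6.3.1.1).

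**Working it through.** The plan gives no figure to reproduce; hypotheses and sample size do not apply. The check compares the two windows and then sizes the gap.

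**1. Windows after the last dose, for a participant who starts new therapy d days later (1 ≤ d ≤ 28)**

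| Event type | Recorded through | Counted as TEAE through |
|---|---|---|
| Nonserious AE | start of new therapy, day d | day 28 |
| SAE | at least day 28 | day 28 |

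**2. Length of the SAE-only tail.** Counting the day therapy starts, the tail is 28 − d + 1 = 29 − d days. The documents do not give d, so these values are assumptions:

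- d = 7: 29 − 7 = 22 days (22/28 = 79%)
- d = 14: 29 − 14 = 15 days (15/28 = 54%)
- d = 28: 1 day
- d > 28, or no new therapy: no tail

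**3. Difference by arm.** SAP 3.2 takes the last dose as the latest non-zero dose of any study drug. Protocol 6.1.2 gives azacitidine on Days 1-7 of a 28-day cycle and glasdegib daily. Assume azacitidine ends on Day 7, glasdegib continues to the day before the switch, and new therapy starts on cycle Day s:

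- Azacitidine alone: the window ends on Day 7 + 28 = 35, so the tail is 35 − s + 1 = 36 − s days, or 0 if s > 35.
- Azacitidine plus glasdegib: last dose is Day s − 1 and the window ends on Day s + 27, so the tail is 28 days.

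| Switch on Day s | Azacitidine alone | With glasdegib |
|---|---|---|
| 15 | 21 days | 28 days |
| 22 | 14 days | 28 days |
| 29 | 7 days | 28 days |
| 36 | 0 days | 28 days |

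If glasdegib stops earlier, the difference shrinks; if both arms switch the same number of days after last dose, it vanishes. Ending the window the day before new therapy stops both arms at Day s − 1 for switches up to Day 36.

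**4. Weight of one participant.** At most 34 participants come from B1371019 and 3 from B1371012, analysed separately (SAP 2.2 and 5.2). Arm sizes are not given.

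- B1371019, arms of 17 (assumed): 1/17 = 5.9%. For a 10/24 split (assumed): 1/10 = 10.0% and 1/24 = 4.2%.
- B1371012: 1/3 = 33.3%.

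**5. Disclosure threshold.** SAP 6.3.1.1 reports nonserious TEAEs occurring in more than 5% of either arm. Since 1/19 = 5.3% and 1/20 = 5.0%, one participant can bring a term over the line in an arm of 19 or fewer. With at most 34 across two arms, at least one arm has 34/2 = 17 or fewer. One unrecorded nonserious event there could drop a term from the disclosed table.

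**The case against.** **A fixed 28-day window is legitimate.** It captures delayed study-drug toxicity, and all-causality tables do not attribute events to a drug. A plain cut would also remove post-switch deaths from the fatal AE summary in SAP 6.3.1.1, the main planned summary of deaths because SAP 6.3.2 is not applicable. This stands, and it shapes the fix. It does not answer the uneven recording within the combined tables.

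**Causality assessment protects the related-event tables.** Partly. Protocol 10.3.3 has investigators weigh concomitant therapy, but SAP 6.3.1 counts unknown causality as related. A reader might infer that every table attributes the next treatment's toxicity to the study drugs; the documents do not support that.

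**The serious-event stream is narrower than it looks.** Protocol 10.3.2 excludes hospitalisation for progression from SAEs and makes progression an SAE only if fatal. Also, serious-only tables do not themselves mix recording periods. Both points stand.

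**The date may be collected.** A reader might infer from the SAP that it is not. The not-applicable entry in SAP 5.3.1 concerns missing dates, and the Schedule of Activities allows additional CRFs, so non-collection is not shown. The SAP still has no rule that uses the date.

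**An external rulebook may supply the rule.** SAP 5.3 cites one for the treatment-emergent algorithm. Its content is not in the documents, and the SAP's explicit definitions contain no cut.

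**Commercial supply.** A reader might infer that everyone who continues azacitidine commercially is affected. The clause is limited to SAE reporting, so whether it ends nonserious recording is ambiguous. A later SAE in that case could also arise on the same drug.

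**Conclusion.** The mismatch is in the current text and should be corrected. It affects the all-causality TEAE tables for participants who start new anticancer therapy within 28 days of last dose: serious and nonserious events are observed over different periods, and SAEs arising under the next treatment are included without a flag. The tail may be longer in the glasdegib arm, under the dosing assumptions shown.

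The documents give neither the number of switchers nor their timing, nor the arm sizes. The tail lengths and the 5.9% are therefore illustrations; only the 34 and 3 maxima, and the consequence that one arm has at most 17, come from the plan. With at most 37 participants and no hypothesis test, this is an inexpensive improvement to the reporting of the sole endpoint. It does not threaten a formal conclusion.

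**What to change.** 1. In SAP 3.3 and 6, end the window for the TEAE summary tables at the earlier of last dose plus 28 days and the day before new anticancer therapy. Note that this refines Protocol 9.4.1.
2. Flag SAEs after that point and list them separately.
3. Keep the serious and fatal AE summaries to last dose plus 28 days, with post-switch events identified, so that no death leaves the tables.
4. Confirm that the new-therapy start date is on the CRF, and add it if not. Restore its derivation in SAP 5.3.1. The general rule for partial start dates takes the first of the month or year, which could precede the last dose, so the restored rule needs the last dose date as a lower bound.
5. Clarify in Protocol 8.3.1.2 whether a switch to commercial supply ends nonserious recording.

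The cost is SAP wording, one clarifying protocol sentence and at most one date field. Some post-switch SAEs are shown separately and not in the combined TEAE tables. SAE reporting to the sponsor's safety group is unchanged.

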8.3.2. Method of Detecting AEs and SAEs

The method of recording, evaluating, and assessing causality of AEs and SAEs and the procedures for completing and transmitting SAE reports are provided in [Appendix 3](#).

Care will be taken not to introduce bias when detecting AEs and/or SAEs. Open-ended and nonleading verbal questioning of the participant is the preferred method to inquire about AE occurrences.

8.3.3. Follow-up of AEs and SAEs

After the initial AE/SAE report, the investigator is required to proactively follow each participant at subsequent visits/contacts. For each event, the investigator must pursue and obtain adequate information until resolution, stabilization, the event is otherwise explained, or the participant is lost to follow-up (as defined in [Section 7.3](#)).

In general, follow-up information will include a description of the event in sufficient detail to allow for a complete medical assessment of the case and independent determination of possible causality. Any information relevant to the event, such as concomitant medications and illnesses, must be provided. In the case of a participant death, a summary of available autopsy findings must be submitted as soon as possible to Pfizer Safety.

Further information on follow-up procedures is given in [Appendix 3](#).

8.3.4. Regulatory Reporting Requirements for SAEs

Prompt notification by the investigator to the sponsor of an SAE is essential so that legal obligations and ethical responsibilities towards the safety of participants and the safety of a study intervention under clinical investigation are met.

The sponsor has a legal responsibility to notify both the local regulatory authority and other regulatory agencies about the safety of a study intervention under clinical investigation. The sponsor will comply with country-specific regulatory requirements relating to safety reporting to the regulatory authority, IRBs/ECs, and investigators.

Investigator safety reports must be prepared for SUSARs according to local regulatory requirements and sponsor policy and forwarded to investigators as necessary.

An investigator who receives SUSARs or other specific safety information (eg, summary or listing of SAEs) from the sponsor will review and then file it along with the SRSD(s) for the study and will notify the IRB/EC, if appropriate according to local requirements.

8.3.5. Exposure During Pregnancy or Breastfeeding, and Occupational Exposure

Exposure to the study intervention under study during pregnancy or breastfeeding and occupational exposure are reportable to Pfizer Safety within 24 hours of investigator awareness.

8.3.5.1. Exposure During Pregnancy

An EDP occurs if:

- A female participant is found to be pregnant while receiving or after discontinuing study intervention.
- A male participant who is receiving or has discontinued study intervention exposes a female partner prior to or around the time of conception.
- A female is found to be pregnant while being exposed or having been exposed to study intervention due to environmental exposure. Below are examples of environmental exposure during pregnancy:
 - A female family member or healthcare provider reports that she is pregnant after having been exposed to the study intervention by ingestion or skin contact.
 - A male family member or healthcare provider who has been exposed to the study intervention by ingestion or skin contact then exposes his female partner prior to or around the time of conception.

The investigator must report EDP to Pfizer Safety within 24 hours of the investigator's awareness, irrespective of whether an SAE has occurred. The initial information submitted

should include the anticipated date of delivery (see below for information related to termination of pregnancy).

- If EDP occurs in a participant or a participant's partner, the investigator must report this information to Pfizer Safety on the CT SAE Report Form and an EDP Supplemental Form, regardless of whether an SAE has occurred. Details of the pregnancy will be collected after the start of study intervention and until 5 terminal half-lives after the last dose.
- If EDP occurs in the setting of environmental exposure, the investigator must report information to Pfizer Safety using the CT SAE Report Form and EDP Supplemental Form. Since the exposure information does not pertain to the participant enrolled in the study, the information is not recorded on a CRF; however, a copy of the completed CT SAE Report Form is maintained in the investigator site file.

Follow-up is conducted to obtain general information on the pregnancy and its outcome for all EDP reports with an unknown outcome. The investigator will follow the pregnancy until completion (or until pregnancy termination) and notify Pfizer Safety of the outcome as a follow-up to the initial EDP Supplemental Form. In the case of a live birth, the structural integrity of the neonate can be assessed at the time of birth. In the event of a termination, the reason(s) for termination should be specified and, if clinically possible, the structural integrity of the terminated fetus should be assessed by gross visual inspection (unless preprocedural test findings are conclusive for a congenital anomaly and the findings are reported).

Abnormal pregnancy outcomes are considered SAEs. If the outcome of the pregnancy meets the criteria for an SAE (ie, ectopic pregnancy, spontaneous abortion, intrauterine fetal demise, neonatal death, or congenital anomaly in a live-born baby, a terminated fetus, an intrauterine fetal demise, or a neonatal death), the investigator should follow the procedures for reporting SAEs. Additional information about pregnancy outcomes that are reported to Pfizer Safety as SAEs follows:

- Spontaneous abortion including miscarriage and missed abortion;
- Neonatal deaths that occur within 1 month of birth should be reported, without regard to causality, as SAEs. In addition, infant deaths after 1 month should be reported as SAEs when the investigator assesses the infant death as related or possibly related to exposure to the study intervention.

Additional information regarding the EDP may be requested by the sponsor. Further follow-up of birth outcomes will be handled on a case by case basis (eg, follow-up on preterm infants to identify developmental delays). In the case of paternal exposure, the investigator will provide the participant with the Pregnant Partner Release of Information Form to deliver to his partner. The investigator must document in the source documents that the participant was given the Pregnant Partner Release of Information Form to provide to his partner.

8.3.5.2. Exposure During Breastfeeding

An exposure during breastfeeding occurs if:

- A female participant is found to be breastfeeding while receiving or after discontinuing study intervention.
- A female is found to be breastfeeding while being exposed or having been exposed to study intervention (ie, environmental exposure). An example of environmental exposure during breastfeeding is a female family member or healthcare provider who reports that she is breastfeeding after having been exposed to the study intervention by inhalation or skin contact.

The investigator must report exposure during breastfeeding to Pfizer Safety within 24 hours of the investigator's awareness, irrespective of whether an SAE has occurred. The information must be reported using the CT SAE Report Form. When exposure during breastfeeding occurs in the setting of environmental exposure, the exposure information does not pertain to the participant enrolled in the study, so the information is not recorded on a CRF. However, a copy of the completed CT SAE Report Form is maintained in the investigator site file.

An exposure during breastfeeding report is not created when a Pfizer drug specifically approved for use in breastfeeding women (eg, vitamins) is administered in accord with authorized use. However, if the infant experiences an SAE associated with such a drug, the SAE is reported together with the exposure during breastfeeding.

8.3.5.3. Occupational Exposure

An occupational exposure occurs when a person receives unplanned direct contact with the study intervention, which may or may not lead to the occurrence of an AE. Such persons may include healthcare providers, family members, and other roles that are involved in the trial participant's care.

The investigator must report occupational exposure to Pfizer Safety within 24 hours of the investigator's awareness, regardless of whether there is an associated SAE. The information must be reported using the CT SAE Report Form. Since the information does not pertain to a participant enrolled in the study, the information is not recorded on a CRF; however, a copy of the completed CT SAE Report Form is maintained in the investigator site file.

8.3.6. Cardiovascular and Death Events

Not applicable.

8.3.7. Disease-Related Events and/or Disease-Related Outcomes Not Qualifying as AEs or SAEs

Not applicable.

8.3.8. Adverse Events of Special Interest

Not applicable.

8.3.8.1. Lack of Efficacy

Lack of efficacy is reportable to Pfizer Safety **only** if associated with an SAE. Refer to [Appendix 3, Section 10.3.1](#) for additional information.

8.3.9. Medical Device Deficiencies

Not applicable.

8.3.10. Medication Errors

Medication errors may result from the administration or consumption of the study intervention by the wrong participant, or at the wrong time, or at the wrong dosage strength.

Exposures to the study intervention under study may occur in clinical trial settings, such as medication errors.

Safety Event	Recorded on the CRF	Reported on the CT SAE Report Form to Pfizer Safety Within 24 Hours of Awareness
Medication errors	All (regardless of whether associated with an AE)	Only if associated with an SAE

Medication errors include:

- Medication errors involving participant exposure to the study intervention;
- Potential medication errors or uses outside of what is foreseen in the protocol that do or do not involve the study participant.
- If the dose administered is >120% of the scheduled dose, <80% of the scheduled dose, or dosed outside a 28 day window. If the drug is administered as incorrect formulation (ie, pills cut in half instead of administering a lower dosage tablet, pills crushed and administered via feeding tube without direction from Sponsor).

Such medication errors occurring to a study participant are to be captured on the medication error page of the CRF.

Medication errors will NOT include:

- Cases where commercial backbone drug was used instead of supplied stock;
- Cases where the wrong lot number of drug was dispensed;
- Dose modifications outlined in [Section 6.6](#).

In the event of a medication dosing error, the sponsor should be notified within 24 hours.

PFIZER CONFIDENTIAL

Whether or not the medication error is accompanied by an AE, as determined by the investigator, the medication error is recorded on the medication error page of the CRF and, if applicable, any associated AE(s), serious and nonserious, are recorded on the AE page of the CRF.

Medication errors should be reported to Pfizer Safety within 24 hours on a CT SAE Report Form **only when associated with an SAE**.

